6.3. Response Evaluable Set

The response evaluable set is defined as patients who have received at least one cycle of study treatment unless discontinued early due to death or PD and have had at least one disease assessment following the initiation of therapy. At least one cycle of study treatment is defined as at least 80% daily treatment compliance at targeted dose level during one cycle (cycle 1 or cycle 2) period prior to the first post-dosing imaging assessment. The response evaluable set will be used for analyses of disease control rate and overall response.

6.4. PK Analysis Set

The napabucasin PK analysis dataset will include all patients who received at least one dose of napabucasin and have at least one quantifiable concentration.

The capecitabine and 5-fluorouracil PK analysis datasets will include all patients who received at least one dose of capecitabine and have at least one quantifiable concentration.

7. DATA HANDLING

7.1. Methods for Handling Missing Dates

For patient data listings, no imputation of incomplete dates will be applied. The listings will present incomplete dates without any change.

Missing or Partial Death Dates

Completely missing death dates will be imputed as the day after the date of last contact.

A death date missing month and day will be imputed as Jan 1st of the year or the date after the date of last contact, whichever comes last.

A death date missing day will be imputed as the 1st of the month or the day after the date of last contact, whichever comes last.

Date of Last Dose of Study Drug

No imputation will be done for first dose date. No imputation will be done for the date of last dose for patients off study. Date of last dose will be imputed by the analysis cutoff date for ongoing patients.

Date of Start of New Anti-Cancer Therapy

Incomplete dates for start date of new anti-cancer therapy will be imputed as follows and will be used for determining censoring dates for efficacy analyses:

- Completely missing start date will be imputed as the day after study treatment failure/relapse/PD, or the end date of new anti-cancer therapy if available, whichever comes first
- Start date missing both month and day will be imputed as Dec 31st of the year , or the end date of new anti-cancer therapy if available, whichever comes first
- Start date missing day will be imputed as the last date of the month, or the end date of new anti-cancer therapy if available, whichever comes first

Missing Dates in Adverse Events/Concomitant Therapies

Every effort will be made to avoid missing/partial dates in on-study data. Start dates of adverse events/concomitant therapies will be imputed as follows:

- Completely missing start date will not be imputed .
- Start date missing both month and day will be imputed as:
 - the date of first dose if the year of the start date is the same as the date of first dose;
 - \circ otherwise, Jan 1st of the year of the start date will be used.

- Start date missing day will be imputed as:
 - the date of first dose if the year and month of the start date are the same as the date of first dose;
 - \circ otherwise, the 1st of the month of the start date will be used.

Stop dates of adverse events/concomitant therapies will be imputed as follows:

- Completely missing stop date will not be imputed.
- Stop date missing both month and day will be imputed as Dec 31st of the year of stop date.
- Stop date missing day will be imputed as the last date of the month of the stop date.

After imputation, the imputed date will be compared against the date of death, if available. If the planned imputed date is later than the date of death, the date of death will be used as the imputed date instead. In any cases above, if the imputed start date is after the end date, then set the start date the same as the end date.

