AEs reported with a relationship to a treatment considered by the investigator to be 'possible', 'probable' or 'definite' will be considered "Related" to BBI608 or a combination drug, respectively. Missing relationship will be considered as "Related". Summaries similar to those for the "all causality AEs" will be provided.

Grade II or above Diarrhea

Number of days of Grade II or above diarrhea will be summarized. For patients who had a Grade II or above diarrhea TEAE ongoing at the time of analysis, the duration of TEAE will be censored at data cutoff or safety follow-up completion date, whichever is earlier. The safety follow-up completion date is the defined as the earlier day of the last treatment plus 30 days and death day (if applicable).

Serious AE and Death

Treatment-emergent SAEs and treatment-related SAEs will be summarized by MedDRA SOC and PT and Maximum CTCAE grade.

Patients who experienced an SAE during the AE reporting period will be listed for all safety patients.

Deaths that occur on the same day or after the first dose of study treatment and within 30 days of the last dose of any study treatment will be summarized. The number and percentage of patients who died during the study treatment and within 30 days after the last dose will be presented.

A listing of death data will include all deaths that occurred during the reporting period for deaths, which starts from the signing of informed consent to the end of the follow-up period. The listing will include date of death, and the number of days relative to the administration of the first and last dose.

Adverse Events of Clinical Relevance

Selected AEs were pre-specified for additional focus due to the potential clinical significance of the event and/or the potential association with the investigational product. These events include those in the standard MedDRA (narrow or broad, as noted) query terms of: non-infectious diarrhea (broad SMQ), gastrointestinal haemorrhage (narrow SMQ), gastrointestinal obstruction (narrow SMQ), acute kidney injury (narrow acute renal failure SMQ) and preferred term of ventricular fibrillation and ventricular tachycardia. Tables listing the incidence, maximum severity and drug relationship of these events in the safety population will be generated.

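### A resolved diarrhea event with a year-only stop date can be counted for longer than one still ongoing, because the duration cap covers only ongoing events and the SAP omits the protocol's two-cycle window

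*SAP*

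**What the plan says.** SAP 7.1 has three rules for the stop date of an adverse event:

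- Month and day missing: "Stop date missing both month and day will be imputed as Dec 31st of the year of stop date".
- Day missing: "Stop date missing day will be imputed as the last date of the month of the stop date".
- Whole date missing: "Completely missing stop date will not be imputed".

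One upper limit follows: "If the planned imputed date is later than the date of death, the date of death will be used as the imputed date instead". Section 7.1 gives no other limit on an imputed stop date.

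SAP 8.2.4.1 then states: "Number of days of Grade II or above diarrhea will be summarized". It gives no time window and names no statistic. It does limit the duration of an event that is "ongoing at the time of analysis, the duration of TEAE will be censored at data cutoff or safety follow-up completion date, whichever is earlier". Safety follow-up completion is the earlier of last treatment plus 30 days and death.

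Protocol 10.8 defines the sub-cohort measures as days of Grade II/III diarrhea and percent compliance, both over the first two cycles. SAP 8.2.1 reports daily compliance over the first 56 days from treatment start. No such window is attached to diarrhea days. SAP 8.2 summarizes data by arm and sub-cohort, and each sub-cohort starts with 6 patients.

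**The concern.** A partial stop date tells us that the event ended. Such an event is not ongoing at analysis, so the limit in 8.2.4.1 does not literally reach it, and only death bounds the imputed date. Less uncertainty about resolution can thus produce a longer counted duration. An unresolved event stops counting at last treatment plus 30 days at the latest. A resolved one with a year-only stop date can run to 31 December, beyond safety follow-up and, if the cutoff falls earlier in that year, beyond the cutoff too.

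The two-cycle window in the protocol would have contained most of this. The SAP carries it over for compliance but not for diarrhea days, which Protocol 10.8 pairs with compliance.

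At stake is the description of tolerability by starting dose and by anti-diarrheal strategy. In a cell of 6, one incomplete date can dominate a mean.

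**Working it through.** **The plan's own figure.** The documents give no figure for the imputation rule. The one number for this measure is the 57% power in Protocol 10.8. Reading 20 as per group, with 0.30 against 0.55, two-sided alpha 0.15 (z = 1.4395) and pooled rate 0.425:

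- Null standard error: sqrt(2 × 0.425 × 0.575 / 20) = 0.1563.
- Alternative standard error: sqrt((0.30 × 0.70 + 0.55 × 0.45) / 20) = 0.1512.
- Power: Φ((0.25 − 1.4395 × 0.1563) / 0.1512) = Φ(0.165) = 56.6%.

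This reproduces. It treats the measure as a proportion and says nothing about how days are counted, so it does not bear on the size of the imputation error.

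**Formula.** False days = imputed stop − true stop. The start date is taken as known and the year as non-leap.

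**Year-end rule.** A true stop on 31 December gives 0 false days and one on 1 January gives 364, or 364/6 = 60.7 on a mean of 6. If true stop dates were uniform over the year (an assumption), the average would be 182, and 73% of stop dates would give at least 100.

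**Example, start 10 March.** From 10 March to 31 December inclusive is 22 + 30 + 31 + 30 + 31 + 31 + 30 + 31 + 30 + 31 = 297 days. That is the whole imputed duration. With an assumed true duration of 5 days, the false part is 297 − 5 = 292 days, and 292/6 = 48.7.

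**Month-end rule.** The maximum is 30 false days (30/6 = 5.0 on a mean of 6). The average is 14.7 under the same uniform assumption.

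**Resolved against ongoing.** Assume first dose on 5 January, onset on study day 8 and a true duration of 5 days, so a true stop on day 12. Treatment lasts 4, 8 or 16 weeks (Protocol 4.6 expects 4 to 16). 31 December is study day 361.

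| Limit applied to the year-only stop date | Last day counted | False days | Added to mean of 6 |
|---|---|---|---|
| SAP as written, patient alive | 361 | 361 − 12 = 349 | 58.2 |
| SAP as written, death on day 180 | 180 | 168 | 28.0 |
| SAP as written, death on day 90 | 90 | 78 | 13.0 |
| Last treatment + 30, 16 weeks | 112 + 30 = 142 | 130 | 21.7 |
| Last treatment + 30, 8 weeks | 56 + 30 = 86 | 74 | 12.3 |
| Last treatment + 30, 4 weeks | 28 + 30 = 58 | 46 | 7.7 |
| First 56 days | 56 | 44 | 7.3 |

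As written, the resolved event counts 361 − 8 + 1 = 354 days in a survivor. An event with the same onset that never resolved counts at most 58 − 8 + 1 = 51, 86 − 8 + 1 = 79 or 142 − 8 + 1 = 135 days for 4, 8 or 16 weeks of treatment. In a sub-cohort extended to 26 patients, the 349 false days add 349/26 = 13.4 to the mean.

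**Bound under the window.** An event that starts inside the first 56 days has at least one true day there, so the error is at most 56 − 1 = 55 days per patient, or 55/6 = 9.2 on a mean of 6. The window does most of the work: it is tighter than last treatment plus 30 days for anyone treated beyond day 26.

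**The case against.** The strongest reply is that the SAP says it is to be read with the protocol. On that reading the two-cycle window still applies and the error cannot exceed 55 days. That is a fair reading, but a programmer working from the SAP finds 56 days written out for compliance and nothing for diarrhea days. The text has to settle it.

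Several limits stand:

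- A year-only stop date may be rare. The SAP promises every effort to avoid partial dates, and adverse events are assessed at repeated visits. The documents give no count.
- Eligibility requires a life expectancy of only 3 months or more, so the death limit will often bind.
- Protocol 10.8 calls the sub-cohort questions exploratory, with extension decided without formal testing, and the SAP tests no hypothesis. Days of diarrhea is not in the SAP's endpoint section; the tolerability objective names the adverse event profile and dose intensity.
- The general list for continuous data in SAP 8.1.3 includes the median and maximum. One extreme record would be visible and would hardly move the median. Listings show partial dates as recorded.

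A reader might infer that any partial stop date adds hundreds of days, or that the sub-cohort comparison will be reversed. The documents do not support either. Only a date missing both month and day can add hundreds, and then only for a stop well before year end in a patient who lives on. Nothing shows that such records exist or fall unevenly between sub-cohorts.

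**Conclusion.** The defect is in the stated rule: for a resolved event with a partial stop date, only death limits the counted days, while the limit written for diarrhea duration reaches ongoing events alone. The size is 0 to 364 false days for a year-only stop date in a survivor and at most 30 for a missing day. The 10 March and 5 January cases rest on an assumed 5-day event, and every shift in a mean assumes one affected patient in a cell of 6.

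The effect is confined to an exploratory tolerability summary and does not touch disease control rate. It is worth correcting because the repair is small and the rule can otherwise give a plainly wrong count.

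**What to change.** Amend SAP 8.2.4.1, in the paragraph on Grade II or above diarrhea:

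1. Count diarrhea days within the protocol's first two cycles, that is, to day 56 from treatment start, as already done for compliance.
2. Apply the existing limit (earlier of data cutoff and safety follow-up completion) to events with an imputed stop date as well as to ongoing events.
3. Repeat the summary without records that have imputed stop dates, as a check.

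Leave SAP 7.1 unchanged for adverse events in general. Protocol 5.5 follows drug-related events to resolution, which can be later than 30 days after the last dose. A general limit in 7.1 could place a stop date before the month or year actually recorded. Limiting the count in 8.2.4.1 leaves the recorded date intact.

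The cost is a few SAP sentences, slightly more programming and one extra table. Diarrhea after day 56 leaves this summary but remains in the adverse event tables and listings.

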7.2. Definition of Baseline Values

Unless otherwise specified, the baseline value is defined as the value collected at the time closest to, but on or prior to, the start of study drug administration. CT and MRI scans may be considered for baseline assessment only if they were performed within 30 days of the first dose of napabucasin.

7.3. Windowing of Visits

All data will be categorized based on the scheduled visit at which it was collected. These visit designators are predefined values as used in the eCRF.

7.4. Withdrawals, Dropouts, Loss to Follow-up

Time to event parameters will be censored if patients withdraw, drop out, or are lost to follow-up before documentation of the events (progressive disease / death). Rules for censoring for PFS are detailed in Appendix 1.3.

7.5. Pharmacokinetics

For individual concentration-time plots and the calculation of PK parameters using noncompartmental analysis, individual below the limit of quantification (BLQ) values will be converted using the following rules:

- If a BLQ value occurs in a profile before the first quantifiable concentration, it will be assigned a value of zero.
- If a BLQ value occurs after a quantifiable concentration in a profile and is immediately followed by a value above the lower limit of quantification (LLQ), then the BLQ value should be treated as missing.
- If a BLQ value occurs at the end of the collection interval (after the last quantifiable concentration) it will be treated as missing.

• If two BLQ values occur in succession after Cmax, the profile will be deemed to have terminated at the first BLQ value and any subsequent quantifiable concentrations will be omitted from PK calculations by treating them as missing.

When imputing BLQ concentrations for the generation of summary statistics at a given time point, all BLQ values will be set to zero except when an individual BLQ falls between two quantifiable values, in which case it will be treated as missing. These same imputations apply to imputation of BLQ concentrations used for generation of concentration-time profiles based on summary statistics.

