### 4 INVESTIGATIONAL PLAN

# 4.1 Overall Study Design

This is an open-label, multicenter Phase II study of oral BBI608 administered with Cetuximab, or Panitumumab, or Capecitabine to patients with advanced metastatic colorectal cancer. The study is based on a Simon 2-stage design that will examine the safety, tolerability and pharmacokinetics of BBI608 and Cetuximab, or Panitumumab, or Capecitabine, and assess the preliminary anti-tumor activity of BBI608 when administered in combination with Cetuximab, or Panitumumab, or Capecitabine in patients with advanced colorectal cancer.

BBI608 treatment will be at a dose level of 480 mg twice daily (960 mg total daily dose). In each cycle, BBI608 will be taken daily continuously for 4 weeks (28 days). BBI608 will be administered twice daily approximately one hour prior to or two hours after meals with the first dose given in the morning and approximately 12 hours between doses.

For patients receiving Cetuximab therapy, Cetuximab will be administered IV on day 5 of cycle 1 at 400 mg/m² intravenous infusion over 120 minutes as the initial dose, then weekly at 250mg/m² over 60-minutes at subsequent cycles.

For patients receiving Panitumumab therapy, Panitumumab will be administered IV on day 8, and 22 of each 28 day cycle at 6 mg/kg over 60 minutes.

For patients receiving Capecitabine therapy, Capecitabine will be administered orally at 1000 mg/m^2 bid daily on days 8-21 every three weeks.

Cycles will be repeated until progression of disease, unacceptable toxicity, or another discontinuation criterion is met. In the case of toxicity, adjustment is permitted. If administration of Cetuximab, or Panitumumab, or Capecitabine is discontinued due to Cetuximab, or Panitumumab, or Capecitabine-related toxicity, administration of BBI608 will be continued until disease progression if tolerated.

Initially, 6 patients will be enrolled in each combination arm at a dose level of 480 mg twice daily (960 mg total daily dose) BBI608. If  $\leq 1$  out of 6 patients has an observable DLT in the combination regimen, then that arm of the study will continue to enroll patients at 480 mg po twice daily (960 mg total daily dose) of BBI608 following the Simon 2-stage design (see Table 1). If

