## 5.3.1.2 Week 1 (Cycle 1, Day 5)

- Karnofsky performance status
- Vital signs (weight, pulse)
- Hematology (see Section 6.3)
- Blood chemistry (see Section 6.3)
- Liver function tests (see Section 6.3)
- Electrolytes (see Section 6.3)
- Urinalysis (see Section 6.3)
- Assess AEs
- Record concomitant medication
- Cetuximab, IV infusion starting about 3 hours after morning dose of BBI608
- The second dose of BBI608 will be given approximately 12 hours after the first dose.
- Blood samples for pharmacokinetics, (for only the first 6 patients enrolled in this arm).
- Dispense BBI608 (one week supply)

Blood samples for pharmacokinetics will be collected immediately prior to the first dose of BBI608 and will continue through 171 hours after administration of the first dose of BBI608. Specific details for the collection of blood samples for pharmacokinetics can be located in Sections 6.4 and Section 16.

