### 10.6 Statistical Analysis of Pharmacokinetic Variables

Pharmacokinetics will only be performed on the first 6 patients enrolled in each combination arm of this study.

Timed blood sample collection for BBI608 and Cetuximab pharmacokinetic analysis will be performed on Days 5-11 and 26-32 after the first dose of Cycle 1 for the first 6 patients enrolled in the Cetuximab arm. Timed blood sample collection for BBI608 and Panitumumab pharmacokinetic analysis will be performed on Days 8-14 and 22-28 after the first dose of Cycle 1 for the first 6 patients enrolled in the Panitumumab arm. Timed blood sample collection for BBI608 and Capecitabine pharmacokinetic analysis will be performed on Days 8-9 and 21-22 after the first dose of Cycle 1 for the first 6 patients enrolled in the Capecitabine arm.

Bioanalytical analysis of patient samples will be conducted at a centralized laboratory using GLP-validated assays. Plasma concentrations will be summarized by descriptive statistics, including mean, standard deviation, coefficient of variation, minimum, maximum, and median.

Concentration profiles will be analyzed by noncompartmental and/or nonlinear least squares regression using WinNonLin. Pharmacokinetic parameters, including  $C_{max}$ , volume of distribution, distribution half-life, terminal half-life, and AUC will be evaluated.

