### Pharmacokinetic Sample Collection (Cetuximab Arm)

### Day 5-12 in CYCLE 1 ONLY

Cycle No.	Procedure	Sample No.	Desired Time
1	Draw blood sample	PK-01	-5 min
	Start BBI608 administration		0 min
	Draw blood sample	PK-02	30 min
	Draw blood sample	PK-03	60 min
	Draw blood sample	PK-04	120 min
	Draw blood sample	PK-05	175 min
	Start Cetuximab infusion		180 min
	Draw blood sample	PK-06	240 min
	Draw blood sample	PK-07	300 min
	Draw blood sample	PK-08	360 min
	Draw blood sample	PK-09	420 min
	Draw blood sample	PK-10	480 min
	Draw blood sample	PK-11	540 min
	Draw blood sample	PK-12	24 hour
	Draw blood sample	PK-13	27 hour
	Draw blood sample	PK-14	99 hour
	Draw blood sample	PK-15	171 hour

Day 26-33 in CYCLE 1 ONLY

Cycle No.	Procedure	Sample No.	Desired Time
1	Draw blood sample	PK-01	-5 min
	Start BBI608 administration		0 min
	Draw blood sample	PK-02	30 min
	Draw blood sample	PK-03	60 min
	Draw blood sample	PK-04	120 min
	Draw blood sample	PK-05	175 min
	Start Cetuximab infusion		180 min
	Draw blood sample	PK-06	240 min
	Draw blood sample	PK-07	300 min
	Draw blood sample	PK-08	360 min
	Draw blood sample	PK-09	420 min
	Draw blood sample	PK-10	480 min
	Draw blood sample	PK-11	540 min
	Draw blood sample	PK-12	24 hour

Draw blood sample	PK-13	27 hour
Draw blood sample	PK-14	99 hour
Draw blood sample	PK-15	171 hour

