### Pharmacokinetic Sample Collection (Capecitabine Arm)

### Day 8-9 in CYCLE 1 ONLY

Cycle No.	Procedure	Sample No.	Desired Time
1	Draw blood sample	PK-01	-5 min
	Start BBI608 administration		0 min
	Draw blood sample	PK-02	30 min
	Draw blood sample	PK-03	60 min
	Draw blood sample	PK-04	120 min
	Start Capecitabine administration		175 min
	Draw blood sample	PK-05	180 min
	Draw blood sample	PK-06	240 min
	Draw blood sample	PK-07	300 min
	Draw blood sample	PK-08	360 min
	Draw blood sample	PK-09	420 min
	Draw blood sample	PK-10	480 min
	Draw blood sample	PK-11	540 min
	Draw blood sample	PK-12	600 min
	Draw blood sample	PK-13	660 min
	Draw blood sample	PK-14	24 hour

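### The BLQ rule in SAP 7.5 ignores that Arm A and B profiles span several napabucasin doses: a BLQ 24 h trough there can be deleted, while the same trough elsewhere is set to zero

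*SAP*

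**What the plan says.** **The rule.** SAP 7.5 has two sets of BLQ rules. One governs individual plots and noncompartmental analysis. The other governs the descriptive summaries, where "all BLQ values will be set to zero except when an individual BLQ falls between two quantifiable values". The excepted value is dropped from the summary. The second set reaches the mean plots too: "These same imputations apply to imputation of BLQ concentrations used for generation of concentration-time profiles based on summary statistics". Neither set mentions samples that lie beyond the next dose.

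**The sampling.** Protocol Appendix D gives the times. In Arms A and B each profile has samples at -5 min, nine or more points up to 540 min, then 24, 27, 99 and 171 h. In Arm C the samples run from -5 min to 660 min, and 24 h is the last.

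**The dosing.** Napabucasin is taken continuously twice a day, "with the first dose given in the morning and approximately 12 hours between doses" (Protocol 4.1). On the PK days, "The second dose of BBI608 will be given approximately 12 hours after the first dose" (Protocol 5.3.1.2, with the same instruction for the other arms).

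**The analytes.** Protocol 10.6 assigns the samples to both drugs; for Arm A, "Timed blood sample collection for BBI608 and Cetuximab pharmacokinetic analysis will be performed on Days 5-11 and 26-32". It does not divide the time points between the drugs.

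**The output.** SAP 8.2.3.1.1 tabulates concentrations by napabucasin dose, partner drug and nominal time, with N, mean, SD, CV, minimum, maximum and median. Protocol 6.4 limits PK sampling to the first 6 patients in each arm.

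**The concern.** Treating a BLQ between two measurable values as missing makes sense after a single dose: once drug has appeared, an isolated BLQ before a later measurable value looks like an assay or sampling fault. It does not make sense when the later measurable value comes from a new dose. A low trough followed by a higher post-dose concentration is then the expected pattern.

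The rule, read as written, can therefore treat the same kind of observation in opposite ways within one patient (-5 min against 24 h) and between arms (A and B against C). One secondary objective is to describe napabucasin PK with each partner drug, and the tables place these means side by side. A difference in 24 h means between arms could then come from the imputation rule and not from the partner drug.

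**Working it through.** The plan states no figure for this rule, so there is none to reproduce. The check applies the rule to the schedules and then sizes the effect.

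**Step 1: where the samples fall.** Doses are at 0, about 12 and about 24 h.
- The 24 h sample is 24 - 12 = 12 h after the evening dose: a trough, if drawn before the morning dose.
- The 27 h sample is 27 - 24 = 3 h after the next morning dose.
- PK days start on Day 5 or later, after continuous dosing from Day 1, so the -5 min sample is a trough too.

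**Step 2: apply the summary rule** to a profile whose troughs are BLQ and whose post-dose samples are quantifiable.

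| Sample | Arms A and B | Arm C |
|---|---|---|
| -5 min (first, nothing before it) | zero | zero |
| 24 h | missing (540 min and 27 h are quantifiable) | zero (last sample) |

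**Step 3: deletion against zero substitution.** Let k of n = 6 troughs be BLQ and let c be the mean of the quantifiable ones. The mean with deletion is c. The mean with zeros is c(6 - k)/6. The ratio is 6/(6 - k):
- k = 0: 1.0, no effect
- k = 1: 1.2
- k = 2: 1.5
- k = 3: 2.0
- k = 4: 3.0
- k = 5: 6.0
- k = 6: no mean can be computed under deletion

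**Step 4: both conventions against the true mean.** Every deleted value lies below the limit and every retained one at or above it, so deletion biases upward and zero substitution downward. The documents give no limit of quantification, half-life or BLQ rate, so the size needs assumptions: lognormal troughs, a limit at the p-th quantile (p = k/6), and expected values. With s = sqrt(ln(1 + CV²)) and z the standard normal p-quantile:
- zero-substituted mean / true mean = Φ(s - z)
- mean with deletion / true mean = Φ(s - z)/(1 - p)

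CV 50% gives s = 0.472; CV 100% gives s = 0.833.

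| BLQ share p | z | Deletion, CV 50% | Zero, CV 50% | Deletion, CV 100% | Zero, CV 100% |
|---|---|---|---|---|---|
| 1/6 | -0.967 | 1.110 | 0.925 | 1.157 | 0.964 |
| 1/3 | -0.431 | 1.225 | 0.817 | 1.345 | 0.897 |
| 1/2 | 0 | 1.363 | 0.682 | 1.595 | 0.797 |

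For example, for p = 1/2 and CV 50%: Φ(0.472) = 0.682, and 0.682/0.5 = 1.363 before rounding.

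**Step 5: the other rule set.** Under the rules for individual plots and noncompartmental analysis, a 24 h BLQ followed by a quantifiable 27 h value is missing in Arms A and B. A terminal 24 h BLQ is missing in Arm C. The arms agree there; only the -5 min value differs, at zero.

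**The case against.** The strongest case against has five parts.

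1. **No BLQ trough may ever occur.** Nothing in the documents shows that any 24 h value will be BLQ. This stands. A reader might infer that the Arm A and B means do read too high; the documents support only that they would if 1 to 5 of 6 troughs were BLQ.

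2. **The factors 1.2, 1.5 and 2.0 are not bias against the truth.** This stands. They compare deletion with zero substitution, which is itself biased low. Read as inflation over the true mean, they overstate it, as Step 4 shows.

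3. **The later samples look like antibody samples.** The infusion starts at 3 h, so 27, 99 and 171 h are 24, 96 and 168 h after it. If napabucasin is not assayed after 24 h, the 24 h sample is last, its BLQ becomes zero and the problem disappears. But Protocol 10.6 and Appendix D assign the sampling to both drugs, the 27 h sample falls within the stated days, and the SAP excludes no napabucasin time point. The possibility is open, not documented.

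4. **Timing and trigger are partly inferred.** Appendix D does not say that the 24 h draw precedes the morning dose; that follows only from twice-daily dosing. The rule is also ambiguous about neighbours. If it means adjacent samples, both 540 min and 27 h must be quantifiable before the 24 h value is deleted. If any earlier and any later value will do, deletion is more frequent. Both limits stand.

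5. **The reach is small and visible.** N is reported at each time point, concentrations are listed, SAP 4.1 plans no hypothesis test, and no decision rule uses a PK mean. This stands and keeps the priority low. A reduced N still does not tell the reader that the lost values were all low ones.

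**Conclusion.** The point holds as a conditional inconsistency of low priority. When a 24 h trough in Arm A or B is BLQ and its neighbours are quantifiable, SAP 7.5 deletes it, whereas the same kind of trough at -5 min in any arm, or at 24 h in Arm C, is set to zero. With some but not all troughs BLQ, the Arm A/B 24 h mean is biased upward and cannot be compared with the pre-dose mean or with Arm C.

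The size depends on a BLQ rate that the documents do not give; the figures against the true mean also rest on the assumed lognormal shape and CV.

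A reader might also infer that the arm contrast carries into the napabucasin PK parameters. The documents do not support that: a 24 h BLQ is missing in all arms under the noncompartmental rules. The contrast is confined to the summary tables and mean profiles.

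**What to change.** Add to SAP 7.5 that the BLQ rules apply within each napabucasin dosing interval: a BLQ counts as lying between two quantifiable values only if both neighbours follow the same napabucasin dose. State that BLQ values at the 24 h trough follow the same convention as at -5 min in all arms, and that later samples belong to later doses. If napabucasin is not assayed after 24 h, say so; that also closes the gap.

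Zero substitution makes the means comparable but leaves them low (0.925, 0.817 and 0.682 of the true mean at CV 50% for 1, 2 and 3 of 6 BLQ). So report the number of BLQ values at each time point and rely on the median, which SAP 8.2.3.1.1 already lists. With six values the median averages the third and fourth in rank, so with zeros in place it is unaffected by up to two BLQ values.

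The cost is a sentence or two in SAP 7.5 and one extra table row. No new data or change in conduct is needed. Any 24 h means in Arms A and B that had dropped BLQ values would become lower.
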